2d.2 Secondary outcome measures

- Outcomes measured by Continuous Glucose Monitor, over 10 days, at baseline and 14-month assessment:
 - Percent time with biochemical hypoglycemia (<54 mg/dL);
 - Number of Level 2 biochemical hypoglycemic events (15 or more minutes <54 mg/dL).
 - Percent time biochemical hypoglycemia (< 70 mg/dL)
 - Number of level 1 hypoglycemic events (≥ 15 minutes at 54 - 69 mg/dL)
 - Number of nocturnal hypoglycemic events (≥ 15 minutes < 70 mg/dL between midnight and 6 am)
 - Percent time 70 to 180 mg/dL
 - Percent time above 180 mg/dL
 - Percent time above 250 mg/dL
 - Average blood glucoses, mg/dL
 - Standard deviation of glucose
 - Coefficient of variation for glucose (%CV)
 - Glucose management indicator
- Outcomes measured by self-report survey at baseline, 6, 10, and 14 months:
 - Number of severe hypoglycemic events in prior 4 months;
 - Hypoglycemia unawareness measured by the single item Gold survey;^{35,36}
 - Number of symptomatic⁴⁸ hypoglycemic events in the prior 4 weeks;⁴⁶
 - Fear of hypoglycemia using the Hypoglycemia Fear Survey-II;⁴⁹
 - Number of nocturnal hypoglycemia events (defined as “during sleep”) during past 6 months;⁵⁰
 - Diabetes and hypoglycemia knowledge with the revised Diabetes Knowledge Test;⁵¹
 - Diabetes self-efficacy using the 8-item Diabetes Self-Efficacy scale.⁵²

- Outcomes defined based on data collected from the EHR:
 - Hemoglobin A1c (HbA1c). The most recent HbA1c measures in the 12 months before baseline will be used for the baseline measure. Most recent measures within the past 3 months will be collected at 14 months. If the participant has not had an HbA1c within the past 3 months at 14 months, they will be asked to have one for the study.
 - Hypoglycemia-related healthcare utilization: total number urgent care, emergency department and inpatient visits for hypoglycemia as primary or principal diagnosis.

Figure 2 shows the relationship between outcome measures and study activities. Due to cost and participant burden, we will collect CGM measures only at baseline and at 14 months. We will measure all secondary outcomes including potential mediators of the intervention, at 6, 10 and 14 months after baseline assessment to identify potential early vs. later effects of the intervention.³²

Outcome Measures and Study Activities

Enrollment call,
Baseline Measures

[figure not shown]

Figure 2: Outcome measures and study activities

2e. Participant timeline

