To retain participants and minimize data loss, we will provide \$100 incentive for completing data collection at baseline and 14 months (\$30 for the survey and \$70 for CGM at each time point) and \$30 for self-report-only measures at 6 and 10 months. Participants who agree to have an HbA1c test for the study at months will receive an additional \$25.

3. Methods: Assignment of interventions

3a. Allocation

After identifying potentially eligible patients based on EHR data, and verify eligibility, documenting verbal consent, collecting baseline data by phone, and receiving written consent, we will randomize study participants to one of our two intervention arms using a 1:1 allocation ratio. Randomization will occur by selecting sequential assignments from randomization sequences generated by the study biostatistician, and stored on a computer inaccessible to study staff. The randomization list will use permuted blocks of randomized size 4 or 8.

Randomization will be stratified by age (18-74 versus 75+ years) and risk score for severe hypoglycemia (moderate versus high risk), to ensure balance of these important risk factors of SH events across intervention arms. Individuals with low risk but using insulin will be randomized in the moderate risk strata. Randomization assignment will be concealed from the study staff verifying eligibility and will only be revealed after baseline data has been collected, and the next sequential randomization assignment has been requested. Outcomes will be measured and analyzed at the participant level.

3b. Blinding (masking)

Blinding or masking will be maintained for research staff collecting outcomes, including those collecting self-report and CGM data. However, participants, nurses, and providers engaged in the interventions cannot reasonably be masked to the study groups, nor can study staff conducting fidelity monitoring or those collecting qualitative data.

The study programmer and biostatisticians will have access to unblinded data to conduct data summaries by intervention group as necessary for reporting to the Data and Safety Monitoring Board (DSMB). The Principal Investigator and other study investigators will remain blinded until all study data for the relevant analyses is collected.

4. Methods: Data collection, management, and analysis

4a. Data collection methods

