Study data will be collected using self-report surveys at baseline, 6, 10- and 14-months; biochemical measures of percent time with hypoglycemia and number of biochemical hypoglycemic events using CGM at baseline and 14 months; and data extracted from the EHR for Hemoglobin A1c and hypoglycemia-related healthcare utilization at baseline and 14 months. The outcomes are described in section 2d, above.

4a.1 Self-report measures:

All self-report instruments are included in **Appendix C**. Survey questions will be administered at baseline and all follow up time points (6, 10 and 14 months) by telephone by trained KPHRI survey research program (SRP) staff. Telephone data collection will be performed using Sawtooth Ci3 and WinCATI computer-assisted telephone interviewing (CATI) software. SRP Interviewers are trained in standardized survey interviewing techniques, use of the CATI system, and will be trained in project-specific procedures including item-by-item specifications for each questionnaire. Interviewers' phone performance, productivity, and response rates are routinely monitored; corrective or remedial training is provided if necessary. Interview quality is continuously assessed using silent monitors installed on all telephones; completed interviews are edited and coded within 48 hours, and interviewer feedback occurs on a regular basis. SRP Interviewers are certified in NIH Human Subjects Protections.

4a.2. CGM data:

CGM data will be collected at baseline and 14 months using the Dexcom 6G Pro CGM integrated sensors and transmitters in blinded mode. We chose Dexcom sensors because of validity, reliability, ability to record glucose measurements blinded to the participant; and the ability to store up to 10 days of data. At both timepoints we will collect 10 days of CGM readings. The readings will be blinded at the time of data collection but shared with the participant at the end of the study.

Baseline CGM data will be collected after collection of baseline self-report data but before beginning any intervention activities. CGM data at 14-months will be collected at the same time as outreach for 14-month follow up self-report. In both cases the process will be the same:

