Participation in this study is voluntary. Even after consent, participants may choose to not do specific study components such as CGM data collection. They may decline survey questions or choose not to participate in intervention activities. Participants will not be considered withdrawn from the study unless they state clearly that they wish to withdraw. For participants who do not complete specific activities but do not withdraw consent, we will continue to use what information they have provided and will extract and use EHR data as described in the consent process. If participants withdraw their consent, we may still use information collected before withdrawal, but will not collect any additional information and will destroy any record of their name or other information that may identify them. This will be clearly stated in the consent materials and reviewed as part of the informed consent process.

4a.6. Process evaluation

In addition to collection of data for primary and secondary outcomes described above, we will conduct a process evaluation to assess whether the interventions were implemented as planned and to test and refine the hypothesized causal pathways (Figure 5). These results will be essential to ensure future implementations of severe hypoglycemia prevention are centered on patient needs and are feasible and acceptable for healthcare providers and systems.

We will use qualitative and quantitative methods for assessing the *fidelity, dose and mechanism* of the intervention.

Qualitative assessments: To assess delivery *fidelity* and *dose* to clusters and individuals, we will observe nurse care managers and diabetes nurse educators working with participants and interview them after interventions.⁵⁷ For observations of nurse care managers, we will develop a tool to capture information on protocol integrity for outreach calls to patients in both comparator groups. We will do observations in the last 2 months of intervention implementation to separate evaluation from earlier fidelity monitoring and feedback training to nurses conducted by the intervention team. We will observe nurses on initial proactive care management outreach calls in each comparator group. We will observe nurses on the two follow-up educational calls in the MyHC-T2D group. We will also observe selected MyHC-T2D group educational sessions facilitated by the diabetes nurse educators.

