Prior to conducting analysis of 14-month outcomes, we will look at the baseline distribution of the self-reported number of severe hypoglycemic events in the prior 12-months collected at baseline. If more than 60% of enrolled patients report 2 or more events, we will revise the primary outcome to be defined as the self-reported *number* of severe hypoglycemic events in the past 12-months, measured at 14-months post baseline (a count rather than a binary outcome and fit a Poisson regression model to estimate the rate ratio for severe hypoglycemia events for the MyHC-T2D group relative to the care management group. We will assess model fit, and consider zero-inflated models as an alternative, if the number of participants reporting zero events violates distributional assumptions of the Poisson model. If primary analyses use the binary outcome measure (i.e. fewer than 60% of patients report 2 or more events in the 12-months prior to baseline), but 40% or more of respondents report 2 or more events at 14-months, we will do a secondary analysis with the count variable as the outcome.

Generalized linear regression models estimated with GEE and robust sandwich errors will also be used to estimate intervention effects on secondary outcomes, with link function and error distribution appropriate for each outcome. For secondary outcomes measured at multiple follow-up time points (6-, 10- and 14-months post-baseline), we will fit a single regression model that includes outcome measures from all follow-up time points. Models will include indicator variables for time, intervention group, and interaction terms between these variables, to estimate intervention effects at each time point. Models will adjust for age, sex, risk score and the baseline measure of the outcome. For hypoglycemia-related health care utilization (urgent care and emergency department visits, hospital admits), we will follow a similar analytic plan as the primary outcome, including the process to determine whether to model these outcomes as binary or count variables.

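### The only glycemic covariate in the HbA1c model is a chart value up to 12 months old at baseline; prespecifying baseline CGM average glucose as a further covariate could regain some of the lost precision.

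*Combined protocol and SAP*

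**What the plan says.** Section 2d.2 defines the baseline HbA1c from the health record: "The most recent HbA1c measures in the 12 months before baseline will be used for the baseline measure". Follow-up is held to a tighter standard: the 14-month value may be no more than 3 months old, and anyone without such a value is invited to take a test. No study test is offered at baseline.

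Section 4c states the covariates for secondary outcomes: "Models will adjust for age, sex, risk score and the baseline measure of the outcome". For HbA1c, the last item is the chart value.

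The trial also plans a 10-day glucose recording at the start. Section 4a.2 says "CGM data will be collected at baseline and 14 months using the Dexcom 6G Pro CGM integrated sensors and transmitters in blinded mode", and section 2d.2 lists "Average blood glucoses, mg/dL" and the glucose management indicator among the CGM measures. Neither enters the HbA1c model.

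Three statements bear on using CGM as a covariate. On timing, section 4a.2 says "Baseline CGM data will be collected after collection of baseline self-report data but before beginning any intervention activities". Section 3a places allocation after "collecting baseline data by phone, and receiving written consent, we will randomize study participants to one of our two intervention arms", without naming CGM as a precondition. On completeness, section 4a.5 says "Even after consent, participants may choose to not do specific study components such as CGM data collection".

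**The concern.** A recent HbA1c is required at the outcome end but not at baseline. The age of the covariate also varies between participants. One route into the trial is a severe episode in the prior 12 months (section 2b), the same window as the chart HbA1c. Section 2c.1 says that usual care after a recent event may include changes to targets or medication. A chart value from before such a change describes an earlier state and is likely to predict the 14-month value less well.

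The stake is the width of the HbA1c confidence interval. HbA1c is the whole of the second key secondary objective (section 1b.2.a), and section 2f gives no power or precision for it. A same-time glucose measure that the trial already plans to collect is left out of the model.

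**Working it through.** **Plan's own figures.** None exists for HbA1c. The sample size behind section 2f does reproduce: 256 × 0.80 = 204.8, stated as 204, or 102 per group. With a two-sided 0.05 test and pooled null variance, power is 90.4% for 60% vs 37.4% (plan: 90%) and 80.8% for 60% vs 40.3% (plan: 80%). Those figures concern the survey-based primary outcome; using 102 per group for HbA1c is an assumption.

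**Gap between covariate and outcome.** Shortest: chart value at month 0, outcome at 14 − 3 = month 11, so 11 months. Longest: chart value at month −12, outcome at month 14, so 26 months.

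**Gain from adding CGM average glucose.** Let r1 be the correlation of chart HbA1c with 14-month HbA1c, r2 that of baseline CGM average glucose with 14-month HbA1c, and r12 that between the two baseline values. All three are assumptions. Age, sex, risk score and session clustering are ignored.

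- Chart value alone: R² = r1².
- Both: R² = (r1² + r2² − 2·r1·r2·r12) / (1 − r12²).
- Residual variance ratio = (1 − R² both) / (1 − R² chart alone).

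| Case | r1 | r2 | r12 | R² chart | R² both | Variance ratio | Reduction |
|---|---|---|---|---|---|---|---|
| Central | 0.5 | 0.5 | 0.6 | 0.25 | 0.3125 | 0.917 | 8.3% |
| Low end | 0.6 | 0.4 | 0.7 | 0.36 | 0.361 | 0.999 | 0.1% |
| High end | 0.4 | 0.6 | 0.5 | 0.16 | 0.373 | 0.746 | 25.4% |

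The low and high rows are the extremes of the grid r1, r2 in {0.4, 0.5, 0.6} and r12 in {0.5, 0.6, 0.7}.

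Central case in detail: (0.25 + 0.25 − 2 × 0.25 × 0.6) / (1 − 0.36) = 0.20 / 0.64 = 0.3125, and 0.6875 / 0.75 = 0.917. The standard error falls by the factor √0.917 = 0.957, so the interval is about 4% narrower. This is worth 204 × (1/0.917 − 1), about 19 participants. The difference detectable with 80% power, (1.96 + 0.84) × √(2/102 × (1 − R²)), moves from 0.340 to 0.325 SD.

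**Share of the loss regained.** Suppose a fresh baseline HbA1c would correlate 0.7 with the outcome (assumption). Its R² is 0.49, so a stale value at 0.5 loses 0.49 − 0.25 = 0.24. Adding CGM in the central case regains 0.3125 − 0.25 = 0.0625, and 0.0625 / 0.24 is about 26%. Other assumed combinations gave about 10% to 80%.

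**Cost of extra terms.** As an approximation, an uninformative covariate costs about 1/204, or 0.5% of precision. Five such terms would cost about 2.5%, more than the gain at the low end of the grid.

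**The case against.** The strongest objection concerns timing. Nothing shows that the baseline CGM is worn before allocation. Section 3a requires the phone survey and written consent, section 4a.2 places CGM after the survey, and section 2d.1 allows 2 months after baseline for both baseline CGM and intervention activities. Figure 4 does not settle the order. Participants are not masked and may decline CGM. If they already know their arm, CGM values or their missingness could differ by arm, and mean fill with an indicator could then introduce bias that the chart value does not carry. This stands and makes the fix conditional. It does not defeat it: section 4c already uses baseline CGM values as covariates for the CGM outcomes, and the age of the chart value is fixed at baseline.

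It is also fair to say that adjusting for the baseline measure of the same outcome is standard, that only one secondary outcome is affected, and that the gain may be negligible. The high end needs a 10-day CGM average to predict 14-month HbA1c better than the chart HbA1c does. All this stands, and it makes the point an optional improvement.

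A reader might infer that the check on whether less hypoglycemia came with worse control rests on HbA1c alone. It does not: section 2d.2 also lists average glucose, the glucose management indicator and percent time above 180 and 250 mg/dL as outcomes, each with its own baseline.

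**Conclusion.** The point holds as a minor matter of efficiency. The HbA1c model relies on one glycemic covariate, 0 to 12 months old at baseline, while a concurrent measure planned by the trial goes unused. Under the assumed correlations, adding it lowers residual variance by about 0% to 25%, with 8% in the central case.

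Four stronger readings are tempting and are not supported:

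- **That the comparison is biased.** A chart value from before randomization, however old, does not bias the randomized contrast.
- **That the model adjusts for nothing but the chart value.** Age, sex and risk score are also included.
- **That CGM would restore all the lost precision.** The documents cannot show this, and the central illustration regains about a quarter.
- **That the change is free.** It needs no new data, but it uses a few degrees of freedom and depends on CGM timing and completeness.

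The size rests wholly on assumed correlations and on carrying the primary outcome's 204 over to HbA1c.

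**What to change.** Before unblinded outcome analysis:

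1. Confirm from study records that the baseline CGM is worn before each participant learns the allocation.
2. If so, prespecify baseline CGM average glucose (or the glucose management indicator) as an added covariate in the HbA1c model, beside the chart HbA1c. Optionally add months from the chart HbA1c to baseline and its product with the chart value, so that older values can carry less weight.
3. If not, use only the chart-age terms in the main HbA1c model and report the CGM-adjusted model as a sensitivity analysis.
4. For missing baseline covariates, whether CGM was declined or no chart HbA1c exists in the 12 months, fill with the overall mean and add an indicator so that no one is dropped. Section 4c gives no specific rule for these cases.

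The cost is a short addition to section 4c, a check of dates already held, and up to about five model terms. If parsimony is preferred, the CGM term with its indicator can be added without the chart-age terms.

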03	10/29/2021	Revised randomization method: covariate constrained randomization instead of matched pair	Allows balance on a greater number of cluster characteristics than matched pair, allows an odd number of clusters.
03	10/29/2021	Self-report data collection will use telephone surveys at all timepoints, not just baseline. There will be no web-based survey collection.	Changed to keep mode consistent, avoid potential mode differences
03	10/29/2021	Revised consent procedures: addition of signed e- or paper consent for participation in the trial	Signed consent required by our Institutional Review Board
04	07/01/2022	Change from cluster to individual randomization	Changes in health care delivery system now allow individual randomization. Individual randomization yields more assurance of comparable balance between study arms and higher likelihood of balanced sample size by arm
04	07/01/2022	Revised inclusion: expand age from >50 to >18	Expands sample to help meet enrollment targets
04	07/01/2022	Expanded recruitment pool to include individuals with type 2 diabetes with current prescription for insulin regardless of Karter risk stratification	Expands screening to help meet enrollment targets. No change to requirement for severe hypoglycemia in past 12 months or current impaired awareness of hypoglycemia.
04	07/01/2022	Update to Study Team: replacement [name] with [name]	Administrative change: [name] has left Kaiser Permanente Washington
05	11/29/2023	Addition of new secondary outcomes of glycemic control	New outcomes consistent with International Consensus on Use of Continuous Glucose Monitoring. Will be important to assess potential

		from Continuous Glucose Monitoring (CGM) data	intervention effects on frequency of high blood sugars and variability of blood glucose levels
05	11/29/2023	Revised plan for mediation analysis	Revised mediation analysis to reflect an updated approach using the causal mediation framework instead of the Baron and Kenney framework
05	11/29/2023	Revised analysis plan for handling missing data	Lowered the threshold for attrition that would trigger use of missing data methods to account for possible selection bias (from 15% to 10%). Other editorial changes to analysis plan were made for clarity, but were not substantive.
06	11/27/2024	Clarified clustering level for analysis	Revised analysis plan to account for patient clustering in the intervention arm within group training session cohorts rather than within clinic.

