- Baseline outreach and engagement in structured educational sessions: KPWA nurses specializing in diabetes will call participants and coordinate care for severe hypoglycemia risk factors as in the proactive care group. Nurses will elicit and address barriers for attending MyHC-TD2 training.⁴¹⁻⁴³ Participants will be mailed the MyHC-TD2 Glucose/Hypo diary and Participant Handbook in preparation for structured educational sessions. They will have the same nurse care manager throughout the intervention.

- Structured Educational Session
1: Two diabetes nurse educators trained on the MyHC-TD2 protocol will lead online virtual group sessions (**Figure 1**). The

[figure not shown]

Figure 1: MyHC-TD2 Education Activities

sessions will include 8 participants and will be conducted based on the Facilitator Guide and Participant Handbooks (**Appendix B**). Educational session #1 will be approximately 3 hours. Nurse educators will encourage participants to reflect on personal hypoglycemia events using the Glucose/Hypo diary. The

session will promote patient understanding and self-management strategies by group discussion of the MyHC-T2D compass points. Diaries will be completed over the first 4 weeks of the study. Daily 4-point and weekly 8-point blood glucose profiles will be done to determine times of increased hypoglycemia risk including at night and allow reflection on possible prevention strategies.

- ***Telephone Review:*** Approximately 2 weeks after the first educational session, nurse care managers will call participants for a 10- to 15-minute review. Nurses will discuss progress and review the Glucose/Hypo diary. They will encourage reflection on any hypoglycemia events and self-management strategies.
- ***Structured Educational Session 2:*** A diabetes nurse educator will lead an online virtual follow-up session with participants in their original groups. This 60-minute session, led by the same diabetes nurse educator as the first session, will facilitate discussion on progress with reference to the 4 points of hypo compass. Participants will be encouraged to reflect on hypoglycemia symptoms experienced during each event including subtle symptoms with review and discussion of the treatments implemented.

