We estimate 256 patients (128 randomized to proactive care management, and 128 randomized to MyHC-T2D) will consent and complete the baseline survey. To account for loss to follow-up, we assume an 80% response rate for the primary outcome measured at 14-months, for an analytic sample size of 204 (102 per group). Power calculations for comparing two independent proportions and assumed a 0.05 type I error rate. Assuming 60% of patients in the proactive care management group will self-report having had a severe hypoglycemia event in 12-month look back (yes/no), we have 90% power to detect a 22.6% absolute difference between groups (i.e. 37.4% severe hypoglycemia rate in MyHC-T2D arm) for the primary outcome. We have 80% power to detect an absolute difference of 19.7% between groups. Our study has power to detect a meaningful difference (30% or more reduction in frequency of self-reported severe hypoglycemia events).⁵⁴ Other studies including for the original *my hypo compass* have similar or larger effects on severe hypoglycemia reductions.²⁵⁻²⁹ We also have 80% power to detect a 1.4% difference and 90% power to detect a 1.6% difference between groups in the secondary outcome of the percent time with biochemical hypoglycemia (<54 mg/dL); this difference is consistent with the effect seen with the original *my hypo compass*.^{25,32}

2g. Recruitment

We will recruit the study population in two steps.

Step 1, Automated risk stratification: We will identify a cohort of adults (≥ 18 years) with T2D receiving primary care at KPWA. We will identify all individuals with either a current prescription for insulin or who have intermediate-to-high risk for a SH event based on our hypoglycemia risk-stratification tool.

Step 2, Phone screening for verbal consent and to identify patients at highest SH risk: We will mail eligible participants an invitation with study brochure and notification that staff will call them about the study. KPHRI Survey Research Program (SRP) members will then call the potential participant to explain the study, assess eligibility and interest, and conduct informed verbal consent with those who are eligible and interested. We expect 1001 eligible. Based on a similar recruitment⁵⁵ and participation in other diabetes education trials, we anticipate at least 25% will consent and complete baseline data collection.⁵⁶

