- **EHR data** will be extracted by the study programmer from automated administrative and EHR data sources, including the KPHRI Data Warehouse, a research-centric repository of datasets maintained by the Research Institute. Data are stored in Teradata, SQL Server, and SAS format and cover enrollment, demographics, diagnoses and procedures, vital signs, pharmacy, lab tests, costs. A rich collection of powerful SAS macros can be used in conjunction with the KPHRI data. KPHRI data warehouse content and usage are documented by a wiki-based system authored by the data warehouse's architects, managers, and users. Access and security for electronic data sources are described below in Section 3. Ethics and Dissemination, Confidentiality.

4c. Statistical methods

Comparative effectiveness analyses will apply intent-to-treat principles, with study participants analyzed based on randomization group, regardless of intervention received. To assess comparability across study groups, we will summarize demographic characteristics and responses to baseline surveys in the two comparison groups. The preliminary analysis plan defines the primary outcome as a binary indicator for whether or not (yes/no) the participant self-reported having had a severe hypoglycemia event in the prior 12-months, assessed 14 months after baseline. We will estimate relative risk of severe hypoglycemia in the MyHC-T2D group vs. proactive care management group by fitting a modified Poisson regression model with the binary self-report measure as the dependent variable and randomization group as the independent variable. Models will adjust for age, sex, risk score, and the number of self-reported severe hypoglycemic events in the 12 months prior to baseline. Models will be fit using generalized estimating equations (GEE) and robust variance estimation to account for correlation due to patient clustering in the intervention arm within group training session cohorts, and the misspecified mean-variance relationship in using Poisson regression for a binary outcome.

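### The 90% and 80% power in section 2f assume independent participants, but section 4c analyses the MyHC-T2D arm as clustered by session cohort; the stated power holds without offsets only if that correlation is very small

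*Combined protocol and SAP*

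**What the plan says.** Section 2f (Sample size) randomizes 128 per arm, applies an attrition allowance ("we assume an 80% response rate for the primary outcome measured at 14-months") and reaches 102 analysed per arm. It describes the method as "Power calculations for comparing two independent proportions and assumed a 0.05 type I error rate". With a 60% control proportion it states 90% power for a 22.6-point difference and 80% for 19.7 points. Attrition is the only adjustment; no ICC, design effect, cohort size or number of cohorts appears.

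Section 2c.2 delivers MyHC-T2D in groups: "sessions will include 8 participants and will be conducted based on the Facilitator Guide". The groups persist: "A diabetes nurse educator will lead an online virtual follow-up session with participants in their original groups", and the second session is "led by the same diabetes nurse educator as the first session".

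Section 4c fits the primary modified Poisson model by GEE with robust variance "to account for correlation due to patient clustering in the intervention arm within group training session cohorts". The version 06 entry in the amendment history shows that this level was chosen deliberately: "Revised analysis plan to account for patient clustering in the intervention arm within group training session cohorts rather than within clinic".

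**The concern.** The power statement describes a simpler design than the one that will be analysed. Participants who share a group of 8, both sessions and a lead educator may have correlated outcomes. Section 4c takes that possibility seriously; section 2f sets it to zero without saying so. Positive correlation raises the variance of the MyHC-T2D proportion and lowers power.

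What is at stake is the reading of the result, especially a null one. Someone who weighs it against 90% or 80% power cannot see that those figures rest on zero cohort correlation.

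**Working it through.** **Inputs.** From section 2f: p1 = 0.60; p2 = 0.374 or 0.403; n = 102 per arm; alpha 0.05. Sidedness is not stated. Two-sided reproduces the plan; one-sided gives 94.8% / 88.3% and does not. From section 2c.2: cohorts of 8, so 128/8 = 16 cohorts and 8 × 0.8 = 6.4 analysed per cohort. Assumed: the ICC, and that every analysed MyHC-T2D participant attended in a full cohort.

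**Formulas.** The design effect applies to the MyHC-T2D arm only: DE = 1 + (6.4 − 1) × ICC.
- SE0 = √[p̄(1−p̄)(1+DE)/102], with p̄ the mean of p1 and p2
- SE1 = √[(p1(1−p1) + DE·p2(1−p2))/102]
- Pooled power = Φ[(p1−p2 − 1.96·SE0)/SE1]
- Unpooled power = Φ[(p1−p2)/SE1 − 1.96]

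**Reproducing the plan (ICC 0, DE 1).** At 22.6 points: (0.226 − 1.96 × 0.06999)/0.06818 = 1.303, power 90.4%. At 19.7 points: (0.197 − 1.96 × 0.07001)/0.06864 = 0.871, power 80.8%. Unpooled: 91.2% / 81.9%. The stated figures are correct for independent groups.

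**With cohort correlation.** Example at ICC 0.05: DE = 1 + 5.4 × 0.05 = 1.27, and (0.226 − 1.96 × 0.07457)/0.07258 = 1.100, power 86.4%. The simulated column uses the planned estimator without covariates: modified Poisson log relative risk, cluster-robust variance, 16 cohorts of 8, beta-binomial outcomes, 80% response, 100,000 trials per cell.

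| Assumed ICC | DE | Pooled, 22.6 / 19.7 points | Unpooled | Simulated | Pooled detectable difference at 90% / 80% power |
|---|---|---|---|---|---|
| 0 | 1.000 | 90.4 / 80.8% | 91.2 / 81.9% | 90.1 / 80.9% | 22.5 / 19.5 points |
| 0.01 | 1.054 | 89.6 / 79.8% | 90.5 / 80.8% | 89.0 / 79.6% | 22.7 / 19.8 |
| 0.02 | 1.108 | 88.8 / 78.7% | 89.8 / 79.8% | 88.4 / 78.3% | 23.0 / 20.0 |
| 0.05 | 1.270 | 86.4 / 75.6% | 87.6 / 76.8% | 85.2 / 74.5% | 23.9 / 20.8 |
| 0.10 | 1.540 | 82.4 / 70.8% | 83.8 / 72.1% | 79.8 / 68.5% | 25.2 / 21.9 |

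**Break-even.** Power equals the stated 90% / 80% at DE 1.026 / 1.041 pooled, that is ICC 0.026/5.4 = 0.005 and 0.041/5.4 = 0.008. Unpooled, DE is 1.093 / 1.099, ICC 0.017 / 0.018.

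**Offsets (pooled).**
- *Response.* With n = 128r and m = 8r, where r is the response proportion, the stated power returns at about 83% / 82% response for ICC 0.02 and 91% / 90% for ICC 0.05. At ICC 0.10 even full response gives 88.2 / 77.9%.
- *Covariates.* A variance reduction of about 3-4%, 10-11% or 20% restores it at ICC 0.02, 0.05 or 0.10. The documents do not quantify this gain.
- *Attendance.* Assume 80% attend and non-attenders carry no session correlation. If cohorts shrink (5.12 analysed attenders each), DE = 0.8 × (1 + 4.12 × ICC) + 0.2, and power is 89.4 / 79.5% at ICC 0.02 and 88.0 / 77.6% at 0.05. If groups are refilled to 8, it is 89.1 / 79.1% and 87.2 / 76.6%.

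**Other power statements.** The subgroup figures in section 4c (39 / 35 and 31 / 27 points) reproduce from 30% and 50% of 102 per arm as independent observations: 39.3 / 34.7 and 31.3 / 27.3. The CGM statement in section 2f gives no standard deviation and mentions no clustering allowance, so it cannot be recomputed.

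**The case against.** The strongest reply is that little follows. The arithmetic is right, the planned analysis already models the correlation, and the summary table at the front lists recruitment as complete, so no wording in section 2f can alter the design. All of this stands, and it limits the point to the power statement.

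The size is also uncertain. No ICC is given, and the values above are assumptions. At ICC 0.01 the shortfall from the stated power is under 0.5 point by either formula. The plan takes no credit for covariates, although "Models will adjust for age, sex, risk score, and the number of self-reported severe hypoglycemic events", and section 4a.5 lets participants skip intervention activities while remaining in the study, which may weaken the clustering. These are fair reasons to show a range. They do not justify leaving the zero unstated, because section 2f claims none of these offsets.

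Four stronger readings are tempting, and the documents do not support them.
- *The trial is underpowered or its inference unsound.* Without an ICC the first cannot be shown, and the section 4c model guards against the second.
- *The stated power has almost no slack.* That is true of the pooled formula (0.4 / 0.8 point), but section 2f names no formula, and the unpooled slack is 1.2 / 1.9 points.
- *The full two-arm design effect applies.* Section 4c places clustering in the intervention arm only; inflating both arms overstates the loss.
- *A small allowance is already built in.* A MyHC-T2D design effect of about 1.03 would also round to 22.6 and 19.7 points, but so small a gap proves nothing, and section 2f states no such allowance.

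**Conclusion.** The point holds as a mismatch between the basis of the stated power and the primary analysis. The 90% and 80% figures are correct for independent participants. For the design in section 4c they are met without offsets only below an ICC of about 0.005-0.008 (pooled) or 0.017-0.018 (unpooled).

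With full attendance and 80% response, power for 22.6 / 19.7 points is about 89-90% / 79-80% by formula at ICC 0.02, with the simulation at 88.4 / 78.3%. Across both formulas and the simulation it is 85-88% / 74-77% at 0.05 and 80-84% / 68-72% at 0.10. The ICC is an assumption throughout. Losses are smaller with non-attendance as modelled above, response above 80%, or covariates that reduce variance. Only the power statement needs correcting.

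**What to change.** Restate section 2f as a partially nested calculation:
- Apply the design effect to the MyHC-T2D arm only, and name the formula (pooled or unpooled, two-sided 0.05).
- State the cohort size, number of cohorts, attendance and response assumptions.
- Give power or detectable difference over a range such as ICC 0.01, 0.02, 0.05 and 0.10, labelled as assumed. Round the figures and check them by simulating the planned GEE estimator, since the simulation falls 1.1-2.6 points below the pooled formula at 0.05-0.10.
- Say that no credit is taken for covariate adjustment.
- Put the CGM power in section 2f and the subgroup power in section 4c on the same basis, or label both as assuming independence.

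The cost is a few sentences in two sections, a short simulation and a slightly less favourable stated power. No patients, data or analysis steps are added or changed.
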